## **4.2 OTHER TREATMENTS, EMERGENCY PROCEDURES, RESTRICTIONS**

### **4.2.1 Other treatments and emergency procedures**

There are no special emergency procedures to be followed.

Stable doses of concomitant therapies for chronic conditions, for which neither the condition nor the treatment are judged to exclude the patient from participation (refer to [Section 3.3](#)) are permissible throughout the duration of the trial. Refer to [Section 4.2.2.1](#) for restrictions with respect to statins, NSBBs / carvedilol and anti-viral treatment for HBV. All concomitant therapy should be carefully evaluated by the Investigator and the Sponsor should be contacted when there are questions.

In case of AEs in need of treatment, any concomitant therapy, based on Investigator's judgement, will be permitted. Diagnostics and treatment should be initiated according to local standard of care.

All concomitant therapies will be recorded on the appropriate pages of the eCRF.

There are no trial-related restrictions regarding COVID-19 vaccination; patients can participate in the trial irrespective of their vaccination status, and vaccination during the trial is also not restricted.

Endoscopic variceal ligation (performed according to local guidelines) is permitted during the trial as required. The procedure should be recorded on the appropriate page of the eCRF.

### **4.2.2 Restrictions**

#### **4.2.2.1 Restrictions regarding concomitant treatment**

The following concomitant therapies must not be administered to patients with diagnosis of NASH entered into treatment group 3 or 4. These restrictions apply from within 5 half-lives after the concomitant therapy has been stopped prior to enrolment (Visit 2), until the EoS visit.

- Other SGLT2 or SGLT-1/2 inhibitors

The concomitant therapies mentioned below must not be co-administered with BI 685509 (also refer to [Table 1.4.2: 1](#)).

- NO-sGC-cGMP pathway activating therapies like NO-donors (e.g. glyceryl trinitrate, isosorbide di- or mono-nitrate, molsidomine), PDE-5-inhibitors (e.g. sildenafil, tadalafil, and vardenafil), non-specific PDE inhibitors such as dipyridamole and theophylline, or sGC-stimulators (e.g. riociguat): These restrictions apply from within 5 half-lives after the concomitant therapy has been stopped prior to enrolment (visit 2), until the EoS visit.

Proprietary confidential information © 2023 Boehringer Ingelheim International GmbH or one or more of its affiliated companies

- Concomitant therapies with a known risk of Torsade de Pointes: These restrictions apply from screening Visit 1a, until the EoS visit. In the event of **temporary** concomitant use of such a therapy, the trial medication must be temporarily stopped and can then be re-started at least 5 half-lives after the concomitant therapy with the known risk of Torsade de Pointes has been stopped. Refer to [Section 4.1.4.2](#) for rules for re-starting up-titration in case of interruption of trial medication.

Co-administration of the following concomitant therapies along with either trial medication, BI 685509 and empagliflozin, is not permitted within 5 half-lives after the concomitant therapy has been stopped prior to enrolment (visit 2), until the EoS visit.

- clinically relevant OATP1B1/3 inhibitors
- clinically relevant concomitant therapies known to inhibit or induce UGT enzymes

In the event of temporary concomitant use of medication that is not permitted, BI 685509 and/or empagliflozin must be temporarily stopped and can be re-started after a period of at least 5 half-lives after the concomitant therapy has been stopped. Refer to [Section 4.1.4.2](#) for rules for re-starting up-titration in case of interruption of BI 685509.

If permanent use of any of the above-mentioned prohibited therapy is required, both trial medications should be stopped.

A list to support the identification of the above-mentioned concomitant therapies will be provided in the ISF. The list will not claim completeness.

Furthermore, patients who are receiving statins, pioglitazone, GLP1-agonists, or vitamin E, must be on a stable dose for at least 3 months prior to screening (Visit 1b), with no planned dose change throughout the trial, and patients who are receiving NSBBs / carvedilol, must be on a stable dose for at least 1 month prior to screening (Visit 1b), with no planned dose change throughout the trial (refer to [Section 3.3.2](#)). In addition, these concomitant therapies should not be initiated during the trial as they will interfere with the efficacy of the trial medication (refer to [Section 3.3.4.1](#)).

If receiving anti-viral therapy for HBV, patients must be on a stable dose for at least 6 months prior to screening, with no planned dose change throughout the trial.

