1. The screening period consists of 3 visits (Visits 1a/b/c). These visits should ideally be completed within a period of 4 weeks, but a maximum of 6 weeks (-42 days) will be permitted. There is no minimum duration. A patient can proceed from one visit to the next as soon as all results from the previous visit are available and if he / she remains eligible for the trial. Visit 1b and 1c can be performed on the same day; in that case, the gastroscopy must be performed prior to the HVPG measurement. The ultrasound [REDACTED] can be performed at either Visit 1b or 1c. Refer to Sections , [5.1.2](#), [5.2.5.1](#), [5.2.5.2](#) and [6.2.1](#)

Proprietary confidential information © 2023 Boehringer Ingelheim International GmbH or one or more of its affiliated companies

2. Visit 2 = enrolment / randomisation / Day 1 of trial medication. All assessments at this visit (excluding post-dose ECGs [redacted] [refer to Sections [5.2.4](#), [6.2](#) and [Appendix 10.1](#)]) should be completed before the first dose of trial medication is administered
3. Patients who complete 8 weeks of treatment will have an End of Treatment (EoT) visit, followed 4 weeks later by an End of Study (EoS) visit. The last dose of trial medication will be administered in the evening of the day before the EoT visit. Patients who discontinue trial medication prematurely will have an Early Discontinuation (ED) visit completed instead of the planned treatment period visit. The ED visit should be performed within 7 days of discontinuing the trial medication, followed 4 weeks later by an EoS visit. Refer to [Section 6.2.2.1](#) for details of assessments that should be performed during an ED visit and the EoS visit that follows it.
4. Fasting status: F = fasting (i.e. overnight fast, no food or drink, except water), NF = non-fasting
5. For further details refer to [Section 6.2.1](#)
6. Anthropometric measures = height (measured at Visit 1a only), weight, and waist and hip circumference. Refer to [Section 5.2.1.1](#)
7. Measurement of vital signs should precede the 12-lead ECG, and measurement of the 12-lead ECG should precede blood sampling and intake of trial medication at visits where a single ECG is required. The 12-lead ECG should be performed after the patient has rested for at least 5 minutes in a supine position. From Visit 2 onwards, the patients home BP monitoring equipment should be used in the clinic to measure vital signs (refer to Sections [5.2.2](#), [5.2.2.1](#) and [5.2.4](#))

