### Residual Effect Period

The Residual Effect Period (REP) of empagliflozin is 7 days. This is the period after the last dose with measurable drug levels and/or pharmacodynamic effects still likely to be present.

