### **3.3.2 Inclusion criteria**

1. Signed and dated written informed consent in accordance with ICH-GCP and local legislation prior to admission to the trial
2. Male or female who is  $\geq 18$  (or who is of legal age in countries where that is greater than 18) and  $\leq 75$  years old at screening (Visit 1a)
3. Clinical signs of CSPH as described by either one of the points below. Each trial patient must have a gastroscopy during the screening period (Visit 1b) or within 6 months prior to screening (Visit 1b). For further details refer to [Section 5.2.5.2](#)
  - (i) documented endoscopic proof of oesophageal varices and / or gastric varices at screening (Visit 1b) or within 6 months prior to screening (Visit 1b)
  - (ii) documented endoscopic-treated oesophageal varices as preventative treatment
4. CSPH defined as baseline HVPG  $\geq 10$  mmHg (measured at Visit 1c), based on a local interpretation of the pressure tracing (refer to [Section 5.1.1](#) for further details)
5. Diagnosis of compensated cirrhosis due to HCV, HBV, or NASH with or without T2DM. Diagnosis of cirrhosis must be based on histology (historical data is acceptable) or on clinical evidence of cirrhosis (e.g. platelet count  $< 150 \times 10^9/L$  [ $150 \times 10^3/\mu L$ ], nodular liver surface on imaging or splenomegaly etc.)

Diagnosis of NASH based on either

  - i. Current or historic histological diagnosis of NASH OR steatosis
  - OR
  - ii. Clinical diagnosis of NASH based on historic or current imaging diagnosis of fatty liver [REDACTED] US, MRI, CT) AND at least 2 current or historic comorbidities of the metabolic syndrome (overweight/obesity, T2DM, hypertension, hyperlipidemia)
6. Willing and able to undergo HVPG measurements per protocol (based on Investigator judgement)
7. If receiving statins must be on a stable dose for at least 3 months prior to screening (Visit 1b), with no planned dose change throughout the trial
8. If receiving treatment with NSBBs or carvedilol must be on a stable dose for at least 1 month prior to screening (Visit 1b), with no planned dose change throughout the trial
9. If receiving pioglitazone, GLP1-agonists, or vitamin E must be on a stable dose for at least 3 months prior to screening (Visit 1b), with no planned dose change throughout the trial

Proprietary confidential information © 2023 Boehringer Ingelheim International GmbH or one or more of its affiliated companies

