### 3.3.3 Exclusion criteria

1. Previous clinically significant decompensation events (e.g. ascites [more than perihepatic ascites], VH and / or overt / apparent HE)
2. History of other forms of chronic liver disease (e.g. alcohol-related liver disease (ARLD), autoimmune liver disease, primary biliary sclerosis, primary sclerosing cholangitis, Wilson's disease, haemachromatosis, alpha-1 antitrypsin [A1AT] deficiency)
3. Patients without adequate treatment for HBV, HCV or NASH as per local guidance (e.g. antiviral therapy for chronic HBV or HCV infection or lifestyle modification in NASH)
  - if received curative anti-viral therapy for HCV, no sustained virological response (SVR) or SVR sustained for less than 2 years prior to screening or if HCV RNA detectable
  - If receiving anti-viral therapy for HBV, less than 6 months on a stable dose prior to screening, with planned dose change during the trial or HBV DNA detectable
  - Weight change  $\geq 5\%$  within 6 months prior screening
4. Must take, or wishes to continue the intake of, restricted concomitant therapy (refer to [Section 4.2.2.1](#)) or any concomitant therapy considered likely (based on Investigator judgement) to interfere with the safe conduct of the trial
5. SBP  $< 100$  mmHg and DBP  $< 70$  mmHg at screening (Visit 1a)

---

A woman is considered of child-bearing potential, i.e. fertile, following menarche and until becoming post-menopausal unless permanently sterile. Permanent sterilisation methods include hysterectomy, bilateral salpingectomy and bilateral oophorectomy. Tubal ligation is NOT a method of permanent sterilisation. A post-menopausal state is defined as no menses for 12 months without an alternative medical cause

Proprietary confidential information © 2023 Boehringer Ingelheim International GmbH or one or more of its affiliated companies

6. Model of End-stage Liver Disease (MELD) score of > 15 at screening (Visit 1a), calculated by the central laboratory
7. Hepatic impairment defined as a Child-Turcotte-Pugh score  $\geq$  B8 at screening (Visit 1a), calculated by the site, using central laboratory results (refer to [Appendix 10.3](#))
8. ALT or AST  $>$  5 times upper limit of normal (ULN) at screening (Visit 1a), measured by the central laboratory
9. eGFR (CKD-EPI formula)  $<$  20 mL/min/1.73 m^2 at screening (Visit 1a), measured by the central laboratory

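### The drug-free interval for NO-sGC-cGMP drugs is counted back from Visit 2, but the only baseline HVPG is taken earlier, at Visit 1c, so it can be measured on a drug that is gone by Week 8

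*Protocol*

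**What the plan says.** **The restriction.** Protocol Section 4.2.2.1 applies one sentence to two drug classes: "These restrictions apply from within 5 half-lives after the concomitant therapy has been stopped prior to enrolment (Visit 2), until the EoS visit". It stands first under other SGLT2 and SGLT-1/2 inhibitors for NASH patients, and is repeated for NO-sGC-cGMP drugs, differing only in a capital letter. The wording is awkward. I read it as requiring 5 half-lives to have passed by Visit 2.

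**Who is kept out.** Exclusion 4 reads "Must take, or wishes to continue the intake of, restricted concomitant therapy". A user who agrees to stop is not excluded by it.

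**When baseline is taken.** Inclusion 4 ties baseline HVPG to the screening visit: "measured at Visit 1c), based on a local interpretation of the pressure tracing". On the length of screening, Flow Chart footnote 1 says: "These visits should ideally be completed within a period of 4 weeks, but a maximum of 6 weeks (-42 days) will be permitted". Section 3.3 allows one re-test during screening but not of HVPG. Protocol Section 7.2.1 and SAP Section 6.7 both take the last value before first dose as baseline, which for HVPG is the Visit 1c value.

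**How other drugs are handled.** For drugs with a known risk of Torsade de Pointes: "These restrictions apply from screening Visit 1a, until the EoS visit". For NSBBs and carvedilol, patients "must be on a stable dose for at least 1 month prior to screening (Visit 1b), with no planned dose change throughout the trial". Statins, pioglitazone, GLP1-agonists and vitamin E have a 3-month stability rule, also tied to Visit 1b.

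**The concern.** The primary endpoint is the percentage change from the Visit 1c HVPG. Protocol Section 3.2 explains that there is no placebo arm, so a change in background treatment between Visit 1c and Week 8 has nothing to cancel against. NO-sGC-cGMP drugs act on the same pathway as BI 685509 (Section 1.2.1), and Section 7.2.2 lists their use as an intercurrent event, so the plan itself treats them as relevant to the endpoint. Stopping one between Visit 1c and Visit 2 is not listed.

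The SAP would not bring such a patient to light. SAP Section 7.3 counts a drug as concomitant if it is ongoing at first dose or starts on treatment; one stopped before Visit 2 is neither. The supplementary analysis in SAP Section 7.4.4 removes only patients with down-titration or interruption. Parts of the SAP around these sections are redacted, so this describes the visible text.

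**Working it through.** **1. Anchors side by side**

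| Drug group | Rule is tied to | Relative to baseline HVPG (Visit 1c) |
|---|---|---|
| Torsade de Pointes risk | Visit 1a | before |
| NSBB / carvedilol | stable 1 month before Visit 1b | before |
| Statins, pioglitazone, GLP1-agonists, vitamin E | stable 3 months before Visit 1b | before |
| NO-sGC-cGMP drugs | 5 half-lives, counted to Visit 2 | may fall after |

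**2. A patient who complies throughout.** Takes a restricted drug at Visits 1a to 1c and is willing to stop, so passes exclusion 4. HVPG at Visit 1c is on the drug. The patient then stops and 5 half-lives pass before Visit 2. The restriction runs to EoS, so Week 8 HVPG is off the drug. No rule is broken.

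**3. The plan's own figures.** Inputs from Protocol Section 7.5: SD 25%, n = 20, threshold 10%.

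SE = 25/√20 = 5.59. P(observed mean reduction ≥ 10%) = Φ((μ − 10)/5.59).

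| True μ | Computed | Stated |
|---|---|---|
| 20% | 96.3% | at least 96.3% |
| 15% | 81.4% | at least 82% |
| 5% | 18.6% | at most 18.8% |
| 0% | 3.7% | at most 3.8% |

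The table reproduces to within 0.6 points.

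**4. Size of the possible shift.** The documents give no HVPG effect for the restricted drugs and no count of users, so both are assumed. Let the stopped drug lower HVPG by d, and let r be the true reduction on BI 685509. With untreated pressure H, baseline is H(1 − d) and Week 8 is H(1 − r), so

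observed reduction = 1 − (1 − r)/(1 − d).

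For r = 20%:

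| Assumed d | Affected patient shows | Mean, 2 of 20 (shift) | P(≥10%) | Mean, 4 of 20 (shift) | P(≥10%) |
|---|---|---|---|---|---|
| 5% | 15.8% | 19.6% (0.4) | 95.7% | 19.2% (0.8) | 94.9% |
| 10% | 11.1% | 19.1% (0.9) | 94.8% | 18.2% (1.8) | 92.9% |
| 15% | 5.9% | 18.6% (1.4) | 93.8% | 17.2% (2.8) | 90.0% |

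Example, d = 10%: 1 − 0.80/0.90 = 11.1%; (2 × 11.1 + 18 × 20)/20 = 19.1%.

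Section 7.5 also calls an observed mean reduction of at least 15% a positive signal. At r = 20% that probability is Φ(5/5.59) = 81.4%. For d = 10-15% it becomes 76.9-74.0% with two affected patients and 71.8-65.1% with four.

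At d = 15%, a patient with a true 20% reduction shows 5.9% and fails the secondary response endpoint (more than 10%). At d = 10% the patient still passes.

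**5. Opposite direction.** If the stopped drug raised HVPG by 10-15%, the affected patient would show 1 − 0.80/1.10 = 27.3% to 1 − 0.80/1.15 = 30.4%. Two of 20 would then raise the mean by 0.7-1.0 points.

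Steps 4 and 5 use the unadjusted group mean. The ANCOVA estimate would differ somewhat, but a baseline covariate does not restore the off-drug baseline.

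**The case against.** **Visit 2 suits the rule's purpose.** The NO-sGC-cGMP restriction is a ban on co-administration with BI 685509, and Section 1.2.1 gives hypotension as the reason. First dose is the natural anchor for that. This stands: the rule is sound for safety. It simply does not also protect the baseline.

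**Few patients may be affected, and the shift is small against the noise.** This also stands. Two patients move the mean by about a quarter of a standard error or less (1.4/5.6), and if the drug lowers HVPG the error works against BI 685509.

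**Moving the anchor has a price.** Patients would stop existing treatment before it is known whether their HVPG qualifies. For that reason no such rule is proposed here.

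A reader might also draw stronger conclusions, which the documents do not support:

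- *That SGLT2 inhibitors share the gap and distort group 3 versus group 4.* The synopsis excludes current or planned SGLT2 inhibitor use, which closes the gap if applied at screening. Section 3.3.3 has no such criterion, so the fault is an inconsistency. Group 4 still receives the class at Week 8. NASH patients with T2DM are randomised after baseline, so prior users are expected in both arms. Assume a 10% SGLT2 effect, a 20% BI 685509 effect, multiplicative and without carry-over. The contrast in naive patients is 28.0 − 20.0 = 8.0 points (1 − 0.8 × 0.9 against 1 − 0.8). In prior users it is 20.0 − 11.1 = 8.9. With 10% prior users in each arm it moves by about 0.09 points. This covers only the randomised patients; group 3 also takes NASH patients without T2DM, who are assigned.
- *That baseline can be six weeks before first dose.* Six weeks limits the whole of screening. Visit 1c follows the results of Visits 1a and 1b, and there is no minimum gap.
- *That the interval conflicts with the residual effect period.* The protocol states: "The Residual Effect Period (REP) of empagliflozin is 7 days". Five half-lives of empagliflozin (10 to 19 h) is 2.1 to 4.0 days. But the rule concerns other SGLT2 inhibitors, and the comparison says nothing about an HVPG taken at Visit 1c or at Week 8.
- *That exclusion 24 needs the same change.* It concerns earlier investigational products in general; nothing in the documents links these to HVPG.

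**Conclusion.** The point holds for NO-sGC-cGMP drugs. The visible text allows a compliant patient to contribute a primary-endpoint baseline taken on a same-pathway drug that is absent at Week 8, and the described analyses would not show it.

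The likely effect is small: about 0.9-1.4 points on a group mean with two of 20 affected, 1.8-2.8 with four, against a standard error of 5.6. These figures rest on an assumed 10-15% lowering of HVPG, assumed counts, a true 20% reduction and the protocol's SD of 25%. The direction depends on the drug. If it lowers HVPG, the BI 685509 effect is understated, so the gap does not by itself produce a false positive signal. The planned sample size and probabilities are unaffected.

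On SGLT2 inhibitors the documents support only the finding that three places disagree.

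**What to change.** 1. **Protocol.** Reconcile the Visit 2 anchor in Section 4.2.2.1 with the Visit 1c baseline HVPG in Section 5.1.1, and say which of the two the drug-free interval is meant to protect. No interval length or stopping rule is proposed here.

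2. **SAP.** From the concomitant-therapy data collected at Visits 1a to 1c, flag patients who were on a restricted NO-sGC-cGMP drug, or within its stated interval, at the baseline HVPG. Report the number per treatment group and repeat the Section 7.4.1 ANCOVA without them, as a further supplementary analysis in Section 7.4.4. Fix the half-lives used for the flag in advance, since the documents do not give them. Partial stop dates can follow SAP Section 6.6.3; setting a missing day to month end will tend to flag too many patients rather than too few.

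   Cost: one derived flag and one extra analysis on slightly fewer patients, with no new data collection.

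3. **SGLT2 inhibitors, separately.** Reconcile the synopsis (current or planned use excluded), Section 3.3.3 (no such criterion) and Section 4.2.2.1 (stopping before Visit 2). Cost: a text correction.

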#### 4.2.2.1.1 Close monitoring for AEs based on concomitant therapy

If a patient is taking concomitant therapy that is metabolised by CYP3A4 and/or CYP2C8, which has a narrow therapeutic index and / or is a sensitive substrate, close monitoring for AEs is recommended in this trial (also refer to [Table 1.4.2: 1](#)). A list to support the identification of the above-mentioned concomitant therapies will also be provided in the ISF. The list will not claim completeness.

#### 4.2.2.2 Restrictions on diet and lifestyle

Drastic changes of diet and lifestyle in the course of the trial should be avoided. This includes unusual and strenuous exercise for the patient (e.g. taking up exercises that put pressure on the abdomen, such as weightlifting).

Alcohol consumption must be avoided throughout the trial; excessive alcohol consumption could lead to hypotension when taken concomitantly with BI 685509.

The requirement for a fasting status upon arrival at clinic visits is as defined in the [Flow Chart](#). Once all visit assessments are complete that require this status, the patient may eat as normal.

#### 4.2.2.3 Contraception requirements

Women of childbearing potential (WOCBP) and men able to father a child must use highly effective methods of birth control per ICH M3 (R2) that result in a low failure rate of less than 1% per year when used consistently and correctly. A list of contraception methods meeting these criteria is provided in the patient information.

WOCBP (for the definition refer to [Section 3.3.2](#)) must be ready and able to use a highly effective method of birth control from the randomisation visit (Visit 2) until 7 days after the last trial medication intake, if their partner is a male able to father a child. No contraceptive is required for the partner of the WOCBP.

Highly effective methods of birth control per ICH M3 (R2) that result in a low failure rate of less than 1% per year when used consistently and correctly include (if local regulations permit):

- combined (oestrogen and progestogen containing) hormonal birth control that prevents ovulation (oral, intravaginal, transdermal)
- progestogen-only hormonal birth control that prevents ovulation (oral, injectable, implantable)
- intrauterine device (IUD) or intrauterine hormone-releasing system (IUS)
- bilateral tubal occlusion

A male patient must use a condom with or without spermicide until at least 7 days after last trial medication intake if their sexual partner is a WOCBP, or, be vasectomised with documented absence of sperm in the ejaculate. No contraceptive is required for the male patient's partner.

Alternatively WOCBP and male patients able to father a child must abstain from male-female sex. This is defined as being in line with the preferred and usual lifestyle of the patient. Periodic abstinence e.g. calendar, ovulation, symptothermal, post-ovulation methods; declaration of abstinence for the duration of exposure to trial medication; and withdrawal are not acceptable.

